NICE - The National Institute for Health and Care Excellence

POP-Q - Pelvic Organ Prolapse Quantification System

Research Protocol

Project Summary

This study will observe participants as they undertake their bariatric journey with the bariatric team. We will assess their urinary symptoms with a questionnaire before their operation and at intervals following their procedure. They will be offered an **optional** vaginal examination also to see if their symptoms correlate with the vaginal examination findings and assess the changes with weight loss. We will conduct semi-structured interviews on a portion of the participants prior to surgery and after. We will **not** be carrying out any surgical interventions ourselves.

PICO Model	Summary			
P articipant	Adult, female participants already with the bariatric services awaiting bariatric surgery.			
Intervention	The participants will undergo bariatric surgery as part of their routine care by the bariatric service			
	We will not conduct surgery ourselves.			
	The interventions involved in the study are questionnaires, interviews and a vaginal examination			
	(optional for the participants).			
Comparison Symptomatic difference between participants before and after having the bariatric surg				
	tools of assessment will be:			
	electronic Personal Health Questionnaires (ePAQ questionnaire)			
	2. An optional vaginal examination			
	3. Psychological interview			
	4. Blood test results available as part of their routine care			
Outcomes	Change in ePAQ questionnaire assessments			
	2. Change in vaginal assessment.			
	3. Qualitative data from the interviews			
	4. Biochemical changes as weight loss occurs			

The project will span eighteen months with three and six monthly intervals for assessments.

Rationale and Background Information

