Obesity has two effect; firstly the direct "physical" effect, but secondly and increasingly recognised, the metabolic effects characterised in "metabolic syndrome" and may help explain why the impact of obesity varies between individuals. The situation is further complicated by the psychological effects firstly associated with developing obesity and secondly the impact of treatment and weight loss. We will also do a systematic review of the literature to look at what is already known about psychological impact of weight loss and effects on their quality of life on LUTS.

With the above in mind, we are interested to have data on the impact of weight loss to better inform women as to the importance of weight loss and it effects on pelvic organ prolapse and female urinary incontinence. Often, a purely surgical approach to conditions does not treat the underlying issues such

as metabolic syndrome as a driver for urgency, and hardly breaches any psychological origin. Our research seeks to gain a better insight into the extent of the role bariatric surgery plays on the pelvic floor regarding patient symptoms and psychological changes. This project is a Prospective Observational Cohort study, following participants undergoing bariatric surgery. We look to assess their urinary symptoms and pelvic floor dysfunction at baseline and at intervals as participants lose weight. The principal tool will be the electronic Personal Health Questionnaires (ePAQ questionnaire), a self-administered electronic smart pelvic floor questionnaire which is validated for use in Urogynaecology. It is widely used within Urogynaecology within the NHS. We will compare the treatment cohort to a group not undergoing surgery.

We will follow the participants up at three, six, nine, twelve and eighteen months following their surgery. Statical analysis will be non-parametric using chi squared. Women who consent will also have a pelvic examination to assess objective changes in any prolapse. In depth qualitative interviews will be conducted to understand how underlying psychological drivers change with particular emphasis on LUTS and based around the responses to the ePAQ questionnaire.

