Tools of assessment	1. Electronic Personal Health Questionnaires (ePAQ questionnaire) and optional vaginal			
	assessments.			
	2. Vaginal assessment using the Pelvic Organ Prolapse Quantification (POP-Q) System			
	3. Interview with questions designed by [name]			
	4. Blood test results - as part of their routine care			
Data Collection	1. ePAQ questionnaire assessments summaries will be available in a qualitative format to assess the			
	different aspects of pelvic floor dysfunction.			
	2. The pelvic examinations will be carried out by a gynaecology trainee under supervision.			
	Recorded semi-structured interviews			
	4. Blood test results – as part of their routine care			
Data analysis	Quantitative data: This data with the scientifically analysed			
	Qualitative data: The data will be analysed using thematic analysis following Braun and Clarke's (2006)			
	model.			

Patient Involvement

We invited patients to review the protocol and patient information leaflet. There was a total of 3 patients; two of them have previously had bariatric surgery and one had a raise BMI and urogynaecology symptoms. All of the patients gave positive feedback and verbal confirmation that the study would be acceptable form their view point.

Methodology

We will recruit participants seen at the bariatric clinic at Heartlands Hospital. This will be alongside their routine bariatric services care.

We seek to recruit 50 women in total (50 women for the quantitative branch of the study and 20 for our qualitative branch). After informed consent, the participants will be initially assessed preoperatively and then followed up at 3, 6, 9, 12 and 18 months post-surgery. Participants will complete an ePAQ questionnaire. Those who consent will be extended to include a vagina assessment. Participants that consent to the qualitative element of the study will undergo a psychological interview.

The participants will be approached by member of the bariatric MDT (i.e. doctors, nursed, dietitians). We will also have posters. The participants will direct to speak to the research trainee who will give the participants more information about the study. The participant will have at least 24 hours to think about taking part and if they agree they will be consented by the research trainee.

Inclusion Criteria

To qualify for NHS foundered weight loss surgery in the Birmingham region, there are strict criteria:

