Following the data collection, if participants are suffering with urinary symptoms and want further help, the participant can ask their GP to refer them to [name] urogynaecology clinic for further assessment, or their local clinician.

IRAS Number: 313247

Data management and statistical analysis

Quantitative data:

Statistical analysis

Initially, analyses will only include data from the immediate preoperative assessment, and subsequent postoperative follow-up assessments. The changes in the severity of LUTS after bariatric surgery will be assessed using a repeated-measures approach. Similar models will then be produced with weight and other participant factors as covariates, in order to identify other factors that are associated with the severity of LUTS. Secondary analyses will also be performed, which additionally include the data from the initial baseline assessments, and subsequent three-monthly assessments, to quantify trends in LUTS over the preoperative period. We will be using the SPSS system to analysis the data.

Sample size calculation

Based on historical clinic flows, it is anticipated that it will be possible to recruit N=50 participants meeting the inclusion criteria. In order to test the viability of this sample size, a statistical power calculation was performed for the primary study aim, namely an assessment of the change in the severity of LUTS between the preoperative and postoperative follow-ups. In the absence of pilot data to estimate the likely distribution of ePAQ scores, a generic power calculation was performed, based on a sign test of the proportions of participants seeing an improvement vs. no change vs. worsening of LUTS between the preoperative and six-month postoperative assessments. It is not anticipated that participants will see a worsening of LUTS as a result of the surgery; hence, the calculation initially assumed 0% of participants would have more severe LUTS at the six-month follow-up, compared to the preoperative assessment. Based on this assumption, the study would be sufficiently powered to detect a success rate (i.e. the proportion of participants with improved LUTS) of 15% at 80% power. If some participants do report a worsening of LUTS, then the minimal detectable difference will increase, as visualised in *Figure 2*. For example, if 10% of participants report a worsening of LUTS postoperatively, then 36% would need to report an improvement in order to detect an effect at 80% power.

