Figure 1 – Study flowchart

[figure not shown]
[figure not shown]

Figure 2 – Sample size calculation

The power calculation was based on a sign test, analysing the change in the severity of LUTS between the preoperative and six-month postoperative assessments, classified as worsening, no change, or improved. Calculations were performed for a sample size of N=50 and alpha of 5%. The trend line represents combinations of the proportions of participants with improved vs. worsened LUTS that would yield 80% power.

Qualitative data

From our qualitative data, the interviews will be transcribed partially by the research team and partly from other professional means. We will analyse what is said in the interviews and language used. We will look at the themes, contact and language used by the participants and analyse.

This will inform the development of a tool kit to identify participants who are at mor risk of psychological distress post-surgery.

Analysis

The audio recordings will be transcribed by the researcher utilising the Jefferson transcription coding to focus upon phonetic and paralinguistic features as well as spoken words, recording what was said and how it was said (Heath & Hindmarsh, 2002). To reduce the occurrence of omissions and mistaken words within the transcripts, the researcher will transcribe each recording within five days of conducting the interview, improving the quality of the transcripts as the memory of what happened during data collection (e.g. body language) rapidly fades (Braun & Clarke, 2013). The data will be analysed using thematic analysis following Braun and Clarke's (2006) model as this is a flexible method. Thematic analysis will be used as a contextualist method, positioned between the two poles of essentialism and constructionism, characterised by critical realism (Willig, 1999).

Missing data: We will be able to identify any missing data/ spurious data will be account for.

Quality assurance

Data Collection: Those involved in collecting data will be GCP trained. The main data collector is a

senior doctor with six years of gynaecology experience. There has been and will be input from [name]

in regards to the qualitative data. In the protocol we have incorporated a standardised protocol for

each interview to ensure that it is a repeatable as possible. We are using a national recognised e-

questionnaire to ensure high quality consistent data is collected. The person undertaking the

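### The background section names chi-squared as the analysis without limit, which does not fit the same women measured before and after surgery and contradicts the repeated-measures analysis and the paired sample size

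*Protocol*

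**What the plan says.** In Rationale and Background Information, directly after listing the follow-up visits, the protocol says: "Statical analysis will be non-parametric using chi squared". It names no outcome, comparison, visit or paired version of the test.

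Under Data management and statistical analysis, the Statistical analysis text says: "The changes in the severity of LUTS after bariatric surgery will be assessed using a repeated-measures approach". It continues: "Similar models will then be produced with weight and other participant factors as covariates".

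The sample size calculation is "based on a sign test of the proportions of participants seeing an improvement vs. no change vs. worsening of LUTS", from the preoperative to the six-month assessment. The caption of Figure 2 repeats this ("The power calculation was based on a sign test") and gives N=50 and alpha 5%.

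The data are repeated measurements on the same people. Methodology says "the participants will be initially assessed preoperatively and then followed up at 3, 6, 9, 12 and 18 months post-surgery", and the comparison row of the Project Summary table begins "Symptomatic difference between participants before and after having the bariatric surg".

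**The concern.** Ordinary (Pearson) chi-squared treats the preoperative and postoperative counts as coming from two separate sets of women. Here they come from one set, so the test uses the wrong standard error for the change. Its p-values are then wrong, and the power claimed for 50 women does not carry over to it.

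The protocol does not say which statement takes precedence. The data-analysis row of the Study design table names no quantitative method, so it does not settle the matter. The dissemination section plans a first analysis at three months and re-analysis every three to six months. With two conflicting methods on record, the choice of test could be made after results have been seen, and that choice can decide whether a result is called significant.

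**Working it through.** **1. Inputs.** From the protocol: N=50; alpha 5% (sidedness not stated, taken as two-sided); scenario A, 15% improved and 0% worse; scenario B, 36% improved and 10% worse; 80% power claimed for both. Assumed, because the protocol does not give them: a yes/no symptom, with improvement meaning that it resolves and worsening that it appears; preoperative prevalence 34-70%. The lower end is the figure the background section cites for incontinence in UK women. Scenario B needs a prevalence of at least 36%, so 50-70% is used there.

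**2. The protocol's own figure.** Write d = improved − worse and D = improved + worse. For the paired sign (McNemar) test by normal approximation:

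power = Φ[(d√N − 1.96√D) / √(D − d²)]

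- A: d = 0.15, D = 0.15. (1.0607 − 0.7591)/0.3571 = 0.845, giving 80.1%.
- B: d = 0.26, D = 0.46. (1.8385 − 1.3293)/0.6264 = 0.813, giving 79.2%.

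Both match the stated 80%, so N=50 rests on a paired test. The exact two-sided sign test gives 78.1% and 74.4%.

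**3. Ordinary chi-squared, scenario A.** Take a preoperative prevalence of 60%, or 30 of 50.

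- With nobody worse, the sign test is significant from 6 improved women (2 × 0.5⁶ = 0.031; 5 women give 0.0625). The chance of at least 6 of 50 at 15% is 78.1%.
- Chi-squared needs a fall of 10 women: 30 to 20 gives z = 0.20/√(0.50 × 0.50 × 2/50) = 2.00, while 30 to 21 gives z = 1.80. The chance of at least 10 of 50 at 15% is 20.9%.

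Simulation in which the preoperative count also varies gives:

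| Preoperative prevalence (assumed) | Chi-squared power | Exact sign test power |
|---|---|---|
| 34% | 32% | 78% |
| 50% | 21-22% | 78% |
| 60% | 21% | 78% |
| 70% | 22% | 78% |

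**4. One data set, two answers.** Let 30 of 50 symptomatic women fall to 22 of 50, with 8 improved and none worse. Chi-squared: z = 0.16/√(0.52 × 0.48 × 2/50) = 1.60, p = 0.11. Sign test: 2 × 0.5⁸ = 0.008.

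**5. Ordinary chi-squared, scenario B.** At prevalence 50-70%, power is about 78-79%, against 74% for the exact sign test. There is no loss here.

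**6. Level under no effect.** With 10% improving and 10% worsening, the variance of the change is 0.20/50 = 0.0040. Chi-squared at 50% prevalence assumes 2 × 0.5 × 0.5/50 = 0.0100, so it is far too cautious. At prevalence 50-70%, simulated rejection is about 0.3-0.5% for chi-squared and about 2.2% for the exact sign test, which is itself below 5% because it is discrete. With 20%/20%, chi-squared rejects in about 3.3-4.5%. Its real level therefore moves with the share of women who change, which is unknown in advance.

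**The case against.** The strongest reply is that the chi-squared sentence is a stray line in the background section, while the section that governs the analysis already gives a valid approach. This largely stands, and it limits the point to a contradiction to be removed. A reader might infer that the protocol fixes chi-squared as its primary analysis; the Statistical analysis section does not support that.

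Other points for the protocol also stand:

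- A reader might count three incompatible methods. There are two. The sign test is used only for sizing, is described as generic for want of pilot data, and is paired like the planned analysis.
- Not every comparison is within women. The background section mentions a group not undergoing surgery, and research question 3a refers to a control group. At a single time point, ordinary chi-squared could be valid there.
- McNemar's test is a chi-squared test for paired data and may have been meant. The text does not say so.
- The loss of power appears in scenario A but not in scenario B.

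None of this makes the sentence correct as written. It is unqualified and directly follows the list of repeated visits.

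**Conclusion.** The point holds as a contradiction in the current text, and that part needs no calculation. The background sentence conflicts with the repeated-measures approach and with the paired basis of the sample size, and ordinary chi-squared does not suit the before and after comparison.

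If it were used, power in the 15%/0% scenario would be about 21-32% instead of about 78-80%. Power in the 36%/10% scenario would be similar. In the pre/post comparisons checked, the error under no effect is towards too few rejections. These sizes depend on the assumed binary symptom and prevalence.

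Two stronger readings are tempting but not supported:

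- Pooling all visits as independent in a between-woman chi-squared would inflate false positives, but the protocol never proposes it. Weight enters as a covariate in the repeated-measures models.
- A repeated-measures analysis that drops every woman with a missed visit is not stated either. The protocol names SPSS but no procedure, and its missing-data sentence ("We will be able to identify any missing data/ spurious data will be account for") specifies no deletion rule.

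**What to change.** Delete the chi-squared sentence from Rationale and Background Information, or restrict it to single-time comparisons with the non-surgical group. State in one place that the preoperative to six-month change in LUTS severity is analysed by the repeated-measures approach already in the Statistical analysis section, with a paired test (sign/McNemar or Wilcoxon signed-rank) for categorised outcomes. A mixed model using all available visits is one suitable form; its detailed specification can be left to a statistical analysis plan.

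The cost is a wording amendment, best made before the three-month analysis. The sample size, the stated power, the data collected and the software do not change.

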- 1. A BMI of more than 35kg/m2 and has type 2 diabetes mellitus which has been diagnosed within the last 10 years or
- 2. A BMI of more than 50kg/m2.

These strict criteria allow an opportunity to study a unique set of participants who are at high risk of having urinary symptoms and pelvic floor prolapse. They would have already undergone weight loss and lifestyle modification methods which would routinely be the first line of action when managing these participants.

The participants in the research study will be

- Female participants over the age of 18
- With a BMI 35mg² and above who have been approved for bariatric surgery but have not yet had treatment.

IRAS Number: 313247

• Able to give informed consent

Eligibility Criteria:

Parameter	Inclusion Criteria	Exclusion Criteria	
Age	>18	<18	
Gender	Female	Male	
Ethnicity	All	-	
ВМІ	>35mg ²	<35mg ²	
Parity	Nulli-parus, Parus	-	
Co-morbidity	-	Dementia/ Inability to consent / Severe Mental health conditions	
Surgery	No previous Bariatric Surgery-	Historic (over 3 months) Bariatric Surgery, previous pelvic floor	
	Or Recent (within 3 months as 1st	surgery	
	follow up is 3 months) Surgery with		
	the weight loss services		
Medications		Diuretics, Anticholinergics	
Bariatric	Qualified for bariatric surgery	Not qualified for bariatric surgery	
Surgery			

Data Collection

Consultation		Quantitative	Qualitative		
1 st consultation	Introductions		Introductions		Introductions
Pre-op Consultation		Optional Vaginal Examination	Qualitative interview with		
		with POPQ	designed questionnaire		
3 months following surgery	ePAQ				
6 months following surgery	Questionnaire	Optional Vaginal Examination	Qualitative interview with		
		with POPQ	designed questionnaire		
9 months following surgery					

12 months following surgery	Optional Vaginal Examination	Qualitative interview with
	with POPQ	designed questionnaire
18 months following surgery		

The initial consultation will be an introduction. This will give us an opportunity to assess the preoperative status of the participants. The women are required to attend follow up and so this will give us an opportunity to follow participants and reassess them.

The data collected will be a combination of quantitative and qualitative data. The quantitative data will compromise of an ePAQ Questionnaire and a vaginal examination with POP-Q assessment. The qualitative data will compromise of a semi structured interview schedule.

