qualitative interviews will undergo training for psychological interviews.

Data Storage: There will be minimal participant information needed. The e-questionnaire will involve

an anonymised weblink to the questionnaire that the patent can log into anonymously. The

questionnaire is hosted on a server withing the N3 spine so securely within the NHS meeting all data

storage requirements of the NHS. Our data collection will be password protected and stored on an

NHS server at Birmingham Women's Hospital. The interviews will be carried out on an encrypted

Dictaphone. All data that have participants details will be securely stored at Birmingham women's

hospital.

Expected Outcomes of the Study.

Overall: We predict that we will have a reasonable uptake of participants for our study. Our biggest

limitation to this is the COVID-19 pandemic and restarting bariatric services to the level prior to COVID-

19. We do not anticipate any adverse incidents. Due to the flexibility of the study, we predict a low

dropout rate as participant can do questionnaires electronically and interviews virtually.

From the known research we predict that there will be an improvement of symptoms as weight loss

occurs. We predict that the participants will have an improvement in self-worth as well as help seeing

behaviours.

Quantitative branch: From the research that is already present we predict that there should be an

improvement of urogynaecology symptoms.

Qualitative branch: We feel that we will see an improvement in participant self-compassion and help

[figure not shown]
seeing behaviours.

Dissemination of results and publication policy

We aim to analyse the three months follow up data for a preliminary result. We with re-analyse the data at three-to-six-month interval till we have completed the eighteen months follow up. We plan to publish the result in peer-reviewed journals. We will produce a summary of the results for the participants to let them know the results. We will aim to present the findings at conferences relating to urogynaecology, bariatric surgery and psychology.

Duration of the project

The project will run for 18 months.

Funding: Not secure yet. Applications have been made. Fortunately, the project is extremely low cost.

IRAS Number: 313247

Project management

[name] - Lead investigator: He will oversee the whole project and give directional support.

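### The stated 18-month project length equals the post-operative follow-up alone, so no woman enrolled before surgery can reach the 18-month visit

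*Protocol*

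**What the plan says.** Two places fix the length of the whole project. Under Duration of the project: "The project will run for 18 months". In the Project Summary: "The project will span eighteen months with three and six monthly intervals for assessments".

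The visit schedule is counted from surgery. Rationale and Background Information says: "We will follow the participants up at three, six, nine, twelve and eighteen months following their surgery". Methodology gives the order of events: "the participants will be initially assessed preoperatively and then followed up at 3, 6, 9, 12 and 18 months post-surgery". The Study design table and the Data Collection table show the same time points. The section on dissemination plans repeated analyses "till we have completed the eighteen months follow up".

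Several steps come before surgery. Methodology says "The participant will have at least 24 hours to think about taking part". The Inclusion Criteria text takes women "who have been approved for bariatric surgery but have not yet had treatment". The Statistical analysis section plans three-monthly assessments to describe trends before the operation, which implies waits of at least three months for some women. The Eligibility Criteria table adds a second route, for women whose operation has already taken place: "Or Recent (within 3 months as 1st" (the cell continues on the next line).

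The text gives no recruitment window, no expected waiting time and no other end-of-study date.

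**The concern.** Eighteen months is exactly the length of the post-operative follow-up. A project of that length leaves no time for finding and consenting 50 women, assessing them before surgery and waiting for the operation. If the stated duration governs, a scheduled assessment cannot be obtained from the women who supply the before-and-after comparison.

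Research question 1c asks whether symptoms relate to the months since surgery. It would lose its last time point, and the later remaining time points could come only from the women operated on earliest. Under slow accrual or long waits, the six-month comparison behind the power calculation would also have fewer than the 50 women it assumes.

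**Working it through.** **Inputs from the protocol.** Project length 18 months (Duration of the project; Project Summary). Visits at 3, 6, 9, 12 and 18 months after surgery. N = 50 and power set at the six-month visit (Sample size calculation).

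**Inputs not in the protocol, assumed here.** Recruitment window R and wait from entry to surgery W, both in months. For the shares below, women enter uniformly over R, all wait W, data collection closes at project month 18, and visits fall on their nominal dates.

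**Step 1: the plan's own figure.** Required duration = R + W + 18. This equals 18 only if R = 0 and W = 0, so the stated figure is not reproduced for any real recruitment period or wait.

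**Step 2: latest operation date for each visit.** A visit v months after surgery needs the operation by project month 18 − v.

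| Visit (months) | Latest operation (project month) |
|---|---|
| 3 | 15 |
| 6 | 12 |
| 9 | 9 |
| 12 | 6 |
| 18 | 0 |

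A woman enrolled before surgery has her operation after month 0, because consent alone takes at least a day. She therefore cannot reach the 18-month visit. This step needs no assumption about R, W or the accrual pattern.

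**Step 3: shares reaching earlier visits.** Share = min(1, max(0, (18 − W − v)/R)).

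| R | W | 6-month visit | 12-month visit | 18-month visit |
|---|---|---|---|---|
| 3 | 3 | 100% | 100% | 0% |
| 6 | 3 | (18−3−6)/6 = 1.5, so 100% | (18−3−12)/6 = 50% | 0% |
| 12 | 3 | (18−3−6)/12 = 75% | (18−3−12)/12 = 25% | 0% |
| 12 | 6 | (18−6−6)/12 = 50% | (18−6−12)/12 = 0% | 0% |

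Of 50 women, 50, 50, 37.5 and 25 are expected at six months in the four rows, and 50, 25, 12.5 and 0 at 12 months.

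**Step 4: the recent-surgery route.** A woman operated on s months before entry (s up to 3) who enters at project month t reaches her 18-month visit at project month t + 18 − s. This is within 18 months only if t ≤ s, so she must enter in the first three months. If s is uniform on 0 to 3, the share of such women who make it is 1.5/R for R of 3 or more: 50% for R = 3, 25% for R = 6 and 12.5% for R = 12. None of them has a study pre-operative assessment.

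**Step 5: duration needed.** R + W + 18 for R = 6 and W = 1, 3, 6 gives 25, 27 and 30 months. For R = 12 it gives 31, 33 and 36 months. Analysis time is extra.

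**Step 6: is the power calculation involved?** A two-sided sign test with N = 50, by normal approximation, gives 80.1% power for 15% improved and 0% worse, and 79.2% for 36% improved and 10% worse. The protocol's figures reproduce under that approximation, so the power calculation is not the source of the problem. It is exposed only if fewer than 50 women reach six months.

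**The case against.** The strongest defence is that 18 months was meant as follow-up per woman. The Project Summary sentence runs the project length together with the assessment intervals, and the dissemination section promises to continue until follow-up is complete. No sentence says that data collection stops at calendar month 18, and the study flowchart is not visible in the text available. This reading is plausible. However, both sentences attach the 18 months to the project, and nothing in the text corrects them, so the wording needs repair even if that was the intent.

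A second point is that the six-month comparison used for power needs only surgery by project month 12, and no research question is tied specifically to month 18. This stands. With 6 months of recruitment and a 3-month wait, every woman reaches six months.

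Three stronger readings are tempting, and the documents do not support them:

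- A reader might infer that nobody at all can reach month 18, or only someone operated on at the very start. The Eligibility Criteria table also admits women operated on within the previous three months, and a few of these could. That route does conflict with the not-yet-treated wording in the Inclusion Criteria text, and the two should be reconciled.
- A reader might infer that the 12-month and six-month results are lost too. That depends entirely on a recruitment window and a wait that the protocol does not state.
- A reader might infer that the time trend is confounded. Cutting follow-up short by entry date biases a within-woman trend only if entry order is related to outcome, or if incomplete follow-up is mishandled. No passage shows that early entrants differ, so this is a possibility and no more.

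**Conclusion.** The point holds as a contradiction inside the protocol. Under the stated project length, none of the women enrolled before surgery can reach the 18-month visit, and that conclusion rests on no accrual assumption. It does take the stated duration as the end of data collection and visits at their nominal dates.

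The size of any earlier loss is conditional. Across the scenarios shown, the share reaching six months runs from 100% down to 50%, and the share reaching 12 months from 100% down to 0%. The protocol calls recruitment its greatest limitation, so the slower scenarios cannot be dismissed, but it gives no figures to choose between them. For question 1c, the final time point is lost for the pre-operative entrants, and later points may rest on the earliest-operated women.

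**What to change.** State three things separately in Duration of the project, and align the Project Summary with them: the recruitment window, the expected wait from entry to surgery, and the end of study. The total should be at least recruitment + wait + 18 months. For recruitment of 6 to 12 months and waits of 1 to 6 months, that is 25 to 36 months, plus analysis time. If 18 months was meant as follow-up per woman, say so in both places and still give the end of study.

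If the project must end at 18 months, remove the 18-month assessment from the schedule and from the planned analyses and claims. Then set an enrolment or inclusion cut-off so that included women can reach the six-month visit. With a wait of W, enrolment would close by project month 12 − W, for example month 9 for a 3-month wait or month 6 for a 6-month wait. The cut-off should apply to entry into the study and not to operation dates, because surgery is routine care outside the study's control. The protocol should also give the numbers then expected at 12 months.

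The first option needs no additional women. It costs a later end date and some staff time, which matters because funding is not yet secured and one research trainee recruits, examines and analyses. The Data Collection table appears to show only the electronic questionnaire at 18 months, but the 12-month visit also carries an optional examination and an interview. The second option costs the 18-month result.
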